1.2. Study Design

Overview of Study Design and Key Features

Phase 2

D: day; EOS: end of study; **SRT**: safety review team; iSRC: internal safety review committee; N: number of participants. Control: licensed influenza vaccine. Refer to Section 4.1 of the protocol for more information.

* Safety review of 7-days post-dosing (Day 8) data of sentinel OA participants by **SRT**/iSRC. Refer to Section 8.3.7.1 of the protocol for details.

** Contact 1 will only be applicable for the first 5 participants in OA groups. Visit 2 (Day 2) will only be applicable for participants in the **CCI** [REDACTED] subset in Phase 2. Remaining Phase 2 participants will not have any contact or visit at Day 2.

*** Visit 3 (Day 8) will be replaced by a Contact for all non-subset participants in Phase 2.

[†]Visit 5 and 6 will be replaced by a Contact if participant has received the standard of care vaccination against seasonal flu after Day 29 prior to this visit and did not report any adverse events that would require physical examination on site.

† Additional blood samples will be collected for a subset of participants in Phase 2.

Design Features	
• Multi-country, multi-center.• Self-contained.• Intended duration of the study per participant: Up to 7 months for participants enrolled in Phase 1 (screening period included) and 6 months for participants enrolled in Phase 2 of the study.• Aspects of data collection: blood samples, safety events, CCI [REDACTED] [REDACTED]• Method of data collection:
– Standardized electronic Case Report Form (eCRF)– Solicited AEs, the occurrence of unsolicited AEs and responses to CCI will be collected using an electronic Diary (eDiary); participants, with support from the site, may install the eDiary application on their own personal, handheld device (e.g.,
------------------------	---

Overview of Study Design and Key Features	
	
mobile phone, tablet) or the site may provide a device that is pre-programmed with the eDiary.
 
 • Safety monitoring: the review of safety data will be performed by an internal Joint Safety Review Team (SRT) and internal Safety Review Committee (iSRC). Refer to Section 8.3.7.1 of the protocol for more information on safety monitoring strategy applicable to this study and Section 10.1.6 of the protocol for SRT and iSRC composition and role. • Dose selection for Phase 2: refer to Section 4.3.2 of the protocol for detailed information on dose selection by an internal Data Review Committee (iDRC) and Section 10.1.6 of the protocol for iDRC composition and role. 
Phase 1:
 
 • Participants aged 18-50 years. • 13 groups enrolled in parallel (12 mRNA groups and 1 control group), detailed in Table 6 of the protocol. • Approximate number of participants: 312 (24 participants per group). • Blinding: single-blind. Refer to Section 6.4 of the protocol for more information on blinding. • Study interventions administered in Phase 1 will be manufactured as separate components and mixed at site by the site staff/pharmacist based on the scheme provided in the Table 6 of the protocol, before dosing each participant. This approach will only be applicable in the Phase 1 part. 
Phase 2:
 
 • Participants aged 18-64 and 65-85 years. • Up to 8 groups enrolled in parallel (up to 3 mRNA groups and 1 control group for each age range), Table 7 of the protocol. Dependent upon immunogenicity data generated in the Phase 1 part of the study, not all mRNA groups may be started. • Approximate number of participants: 960 (120 participants per group). Dependent upon immunogenicity data generated in the Phase 1 part of the study, not all mRNA groups may be started which would reduce the planned number of participants. • Blinding: observer-blind. Refer to Section 6.4 of the protocol for more information on blinding. • An CCI [REDACTED] will be defined for additional immunogenicity analyses and will consist of approximately 50 participants of each group (Flu mRNA and Control). • Final number of groups, number of participants, and dose levels will be described in a protocol amendment prior to initiation of the Phase 2 part of the study.
Study intervention	
All study interventions are administered as single-dose intramuscularly (IM).
 
 • Up to 12 mRNA formulations may be assessed in phase 1 (refer to Table 6 of the protocol) while up to 3 mRNA formulations are expected to be assessed within each age group in Phase 2 (refer to Table 7 of the protocol). • CCI [REDACTED] [REDACTED] [REDACTED] [REDACTED] [REDACTED] [REDACTED]

Overview of Study Design and Key Features	
	
 • CCI [REDACTED] [REDACTED] [REDACTED] [REDACTED] [REDACTED]
Study intervention Assignment	
All participants will be centrally assigned to randomized study intervention using an automated Internet-based system. Once a participant identification number is allocated, the randomization system will determine study group and will provide the study intervention number to be used.
 
 • In Phase 1 of the study, the randomization algorithm will use a minimization procedure accounting for sentinel status as a stratification factor, and study, country, center, and flu vaccination history during past 2 years as minimization factors. • For Phase 2, the randomization algorithm will use a minimization procedure accounting for age group and sentinel status (in OA group only) as a stratification factors, and study, country, center, and flu vaccination history during past 2 years as minimization factors. In addition, CCI [REDACTED] [REDACTED] [REDACTED] 
In the randomization algorithm, allocation within the levels of the minimization factors will be based on equal weights.

Interim Analysis	
In addition to the analyses detailed below, additional analyses e.g., safety analyses, may be conducted to support the SRT, iSRC and iDRC decisions, as described in Section 8.3.7.1 of the protocol. Refer to Section 10.1.6 of the protocol for the SRT, iSRC and iDRC roles.
 
Two interim analyses are foreseen and will be conducted upon availability of all primary endpoints up to Day 29 for participants in Phase 1 and Phase 2, respectively. The interim analysis in Phase 2 will serve to inform future Phase 3 study(ies) preparation.

2. STATISTICAL HYPOTHESES

There is no formal hypothesis testing in this study; where statistical methods are applied, the emphasis will be on estimation with 95% CIs.

2.1. Multiplicity Adjustment

As this study is descriptive, no adjustment for type 1 error will be done.

3. ANALYSIS SETS

Analysis Set	Definition / Criteria	Analyses Evaluated
Screened	All participants who were screened for eligibility.	Screening failure
Enrolled	All participants who entered the study (who were randomized or received study intervention or underwent a post-screening study procedure). Note: screening failures (who never passed screening, even if rescreened) and participants screened but never enrolled into the study (met eligibility but not needed) are excluded from the Enrolled analysis set as they did not enter the study.	Study population
Exposed Set (ES)	All participants who received a study intervention. Analysis per group is based on the study intervention administered.	Safety, immunogenicity if applicable, demography
Per Protocol Set (PPS)	All eligible participants who received the dose of study intervention as per protocol, had immunogenicity results pre- and Day 29 post-dosing for at least one CCI [REDACTED], without intercurrent conditions (influenza disease, new malignancy and immunocompromised condition) that may interfere with immunogenicity and without prohibited concomitant medication/vaccination before Day 29. The analysis will be done according to the study intervention that participants received. Results from blood sample deviating from the dosing/blood draw intervals (refer to Table 9 and Table 10) as well as results obtained after intercurrent conditions (influenza disease, new malignancy and immunocompromised condition) that may interfere with immunogenicity or after prohibited concomitant medication/vaccination during this period will be excluded from the PPS.	Immunogenicity, demography

4. STATISTICAL ANALYSES

4.1. General Considerations

All statistical analyses will be performed using SAS® software Version 9.4 or later.

Missing data will not be imputed unless mentioned otherwise (refer to Section [6.2.2](#)).

Participants will be analysed according to the age group stratum that was used at the time of randomization but with the actual vaccine received. For other minimization factors, the actual value will be considered for analysis.

4.1.1. General Methodology

Enrolled participants who withdraw from the study will not be replaced.

Continuous data will be summarized using descriptive statistics (n, mean, standard deviation, median, interquartile range, minimum, and maximum). Categorical data will be summarized using the participant count and percentage for each category.

A row denoted “Missing” will be included in count tabulations where specified on the shells to account for dropouts and missing values.

The denominator for all percentages will be the number of participants with non-missing values of corresponding parameter in that study group within the analysis population of interest, unless otherwise specified.

Confidence intervals (CIs) will use 95% confidence levels.

For calculations regarding functional titers, values reported as below a quantifiable threshold will be replaced by half the threshold while values above a quantifiable threshold will be assigned the value of the threshold.

For calculations regarding polypositive ~~CCI~~ frequencies, frequencies below 590 per 10^6 cells will be replaced by 590.

A table, figure, listing (TLF) is to be generated for any required item even where no data is available or reported. In such cases, except for table presenting percentage of participants which will show 0%, the table, figure, or listing will state: “No Data Reported”. This will confirm to the health authorities that all data for the tables, figures, listings, and narratives are accounted for.

4.1.2. Baseline Definition

Baseline will be defined as the last non-missing evaluation prior to study intervention administration, unless otherwise specified.

4.2. Primary Endpoint(s) Analyses

4.2.1. Reactogenicity and Safety Endpoints

The analysis of reactogenicity and safety endpoints will be based on the ES. All analyses will be done separately for OAs and YAs according to study phase, unless specified otherwise.

4.2.1.1. Solicited AEs

All solicited events must be recorded into the eDiary during the first 7 days following administration of the dose of study intervention (Day 1 to Day 7 included), irrespective of occurrence or intensity. Solicited events ongoing after Day 7 will continue to be recorded into the eDiary from Day 8 to Day 28 and followed-up until the event has resolved, subsided, stabilized, disappeared, or until the event is otherwise explained, the participant is lost to follow up, or study is completed.

The following administration site events will be solicited:

- Pain
- Redness

- Swelling
- Lymphadenopathy, defined as localized axillary, cervical or supraclavicular swelling or tenderness ipsilateral to the injection arm.

The following systemic events will be solicited:

- Fever
- Chills
- Headache
- Fatigue
- Myalgia
- Arthralgia

Note: Participants will be instructed to measure and record the axillary temperature in the evening. If additional temperature measurements are taken at other times of the day, participants will be instructed to record the highest temperature in the eDiary.

Grading or actual temperature/redness and swelling will be captured in the eDiary as per a modified grading of symptoms based on the FDA toxicity grading guidance for industry [FDA, 2007] with Grades 3 and 4 combined except for fever (refer to Section 6.2.2.3). When available, solicited AE information (e.g., occurrence, grading) collected by study staff when daily eDiary is missing/incorrect will be used in these summaries.

The percentage of participants reporting each individual solicited administration site event (any grade, Grade 2 or 3, Grade 3 and medically attended events) and solicited systemic event (any grade, Grade ≥ 2 , Grade ≥ 3 and medically attended events) within the 7-day follow up period (i.e., Day 1-Day 7 post-dosing) will be tabulated for each group according to the maximum grading in Day 1-Day 7.

The same summaries will be generated for any, administration site solicited AEs, any systemic solicited AEs and any solicited AEs.

The duration of solicited AEs of any grade (see Section 6.2.1.9) will be summarized. The start date is the first day during the 7-day solicitation period with the symptom at grade > 0 while the stop date is the last day with the symptom at grade > 0 in or beyond the solicited period. In addition, the duration for specific grade(s) for each symptom defined as the number of days in the reporting period with grade above or equal to specific grade will be summarized.

Prolonged solicited AEs that continue beyond Day 7 or Day 28 will be identified using a flag in listing of AEs.

The number of completed eDiary days in the solicited period for a participant will be summarized by study group using frequency table.

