### 10.3.4. Unsolicited AE

Definition of unsolicited AE

 
An unsolicited AE is an AE that was either not included in the list of solicited events or could be included in the list of solicited events but with an onset outside the specified period of follow up for solicited events. Unsolicited AEs must have been communicated by participants who has signed the informed consent or through his/her caregiver. Unsolicited AEs include both serious and non-serious AEs.
 
Potential unsolicited AEs may be medically attended (i.e., symptoms or illnesses requiring a hospitalization, emergency room visit, or visit to/by a healthcare provider). Upon notification from eDiary system to the investigator of the occurrence of unsolicited AEs that are medically attended or perceived as a concern by the participant, the site should contact the participant to collect the safety information as soon as possible. Detailed information about reported unsolicited AEs will be collected by qualified site personnel and documented in the participant's records and entered into eCRF.
 
Unsolicited AEs that are not medically attended nor perceived as a concern by the participant will be collected during an interview with the participant and by review of available medical records at the next visit/contact and documented in the participant's records and entered into eCRF.
 
Site staff should monitor participants compliance to completion of eDiary on ongoing basis based on eDiary web-reporting portal and/or automated alerts sent by e-mail. During unsolicited reporting period, if eDiary was not submitted by a participant for a day, site should attempt to contact the participant in timely manner to re-train on importance of eDiary compliance and to collect information about AEs, if any.
 

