#### **10.3.5.2. Time period for collecting and recording AEs, SAEs, AESIs and pregnancies**

Occurrence of unsolicited events will be recorded in to eDiary within 28 days after administration of the study intervention (Day 1 to Day 28). An automatic reminder to complete the eDiary will be sent to the participants/caregivers during this timeframe. Unsolicited AE information must be recorded into the appropriate Section of the eCRF, irrespective of their intensity or whether or not they are considered related to the study intervention.

All solicited events that occur during 7 days following administration of the dose of study intervention (Day 1 to Day 7 included) must be recorded into the eDiary, irrespective of intensity. Solicited events ongoing after Day 7 will continue to be recorded into the eDiary from Day 8 to Day 28 and followed-up until the event has resolved, subsided, stabilized, disappeared, or until the event is otherwise explained, the participant is lost to follow up, or study is completed.

All other AEs occurring within this time frame should be recorded into the appropriate Section of the eCRF, irrespective of their intensity or whether or not they are considered related to the study intervention.

Refer to Section 8.4.1 for more information on collection and reporting of safety information in this study.

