4.2.1.2. Unsolicited AEs

An AE is any untoward medical occurrence in a clinical study participant, temporally associated with the use of a study intervention, whether or not considered related to the study intervention. An AE can therefore be any unfavorable and unintended sign (including an abnormal laboratory finding), symptom, or disease (new or exacerbated) temporally associated with the use of a study intervention.

The verbatim reports of unsolicited AEs will be reviewed by a qualified person and the signs and symptoms will be coded according to the Medical Dictionary for Regulatory Activities (MedDRA) Dictionary for Adverse Reaction Terminology. Every verbatim term will be matched with the appropriate Preferred Term (PT).

A study intervention causally related AE is defined as an AE for which the investigator classifies the possible relationship to study intervention as “Yes”. Investigators will not be required to assess the causality of solicited AEs if the onset is during the solicitation period.

The investigator is obligated to assess the relationship between study intervention and each occurrence of each AE/SAE/device deficiency. The investigator will use clinical judgment to determine the relationship.

The percentage of participants with any unsolicited AEs within the 28-day follow up period (i.e., Day 1-Day 28 post-dosing) with its exact 95% confidence interval (CI) will be tabulated by group and by MedDRA PT and System Organ Class (SOC). Similar tabulation will be done for Grade 3 unsolicited AEs, for any causally related unsolicited AEs, for Grade 3 causally related unsolicited AEs and for unsolicited AEs resulting in a medically attended visit.

In the AE summaries, a participant with 2 or more AEs within the same SOC or PT level but different relationship will be counted only once in the level using the related incident.

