6.2.1.10. Counting Rules for Occurrences of Solicited and unsolicited Events

When the occurrences of solicited events are summarized, each event recorded as having occurred during a specific period will be counted as only 1 occurrence regardless of the number of days on which it occurs.

Accordingly for the summary presenting the number and percentage of participants reporting any solicited and unsolicited adverse events excluding SAE, a solicited AE starting within the solicited period (day 1-7) will be counted as one event while unsolicited AE, excluding prolonged solicited AE will be counted as different event when these are associated to different MedDRA Primary Term or different start date. For instance, a participant with fatigue for several days within the solicited period, with fatigue prolonged beyond the solicited period and with fatigue restarting later in the unsolicited period will contribute as 2 occurrence of fatigue.

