6.2.2.4. Unsolicited Adverse Events

Unsolicited adverse event summaries are including serious adverse events unless specified otherwise.

For the summary of unsolicited adverse events, ongoing solicited events reported as unsolicited AEs will not be counted.

Missing severity, relationship with study intervention, and outcome of unsolicited adverse events will not be replaced and will appear as 'UNKNOWN' when displayed in a statistical output.

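### A continuous solicited event that begins by Day 7 but first reaches Grade 3 on Day 8-28 is in neither the solicited nor the unsolicited Grade 3 endpoint tables

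*SAP*

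**What the plan says.** The co-primary reactogenicity endpoint is the occurrence of solicited events from Day 1 to Day 7 (Protocol Table 5, SAP Table 1). SAP 4.2.1.1 plans rows by grade, for example each "solicited systemic event (any grade, Grade ≥ 2 , Grade ≥ 3 and medically attended events) within the 7-day follow up period", and these percentages "will be tabulated for each group according to the maximum grading in Day 1-Day 7". The composite rows (any administration-site, any systemic, any solicited event) are built the same way.

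Collection does not stop at Day 7. Protocol 10.3.5.2 states: "Solicited events ongoing after Day 7 will continue to be recorded into the eDiary from Day 8 to Day 28". SAP 4.2.1.1 repeats this.

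For unsolicited AEs over Day 1-28, SAP 4.2.1.2 adds severity tables: "Similar tabulation will be done for Grade 3 unsolicited AEs", and likewise for related Grade 3 events. SAP 6.2.2.4 then restricts what enters them: "For the summary of unsolicited adverse events, ongoing solicited events reported as unsolicited AEs will not be counted". This agrees with Protocol 10.3.4, where a listed symptom is unsolicited only if it "could be included in the list of solicited events but with an onset outside the specified period of follow up for solicited events". It also agrees with SAP 6.2.1.10, under which "a solicited AE starting within the solicited period (day 1-7) will be counted as one event while unsolicited AE, excluding prolonged solicited AE", is counted separately only when the MedDRA term or start date differs.

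Two further outputs in SAP 4.2.1.1 touch events that run past Day 7. One is a listing flag for events continuing beyond Day 7 or Day 28. The other is a grade-specific duration, for which the "number of days in the reporting period with grade above or equal to specific grade will be summarized". The reporting period is not defined.

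**The concern.** Each rule is reasonable alone. The 7-day grading window matches the endpoint, and the exclusion from the unsolicited tables avoids counting one event twice. Together they leave a gap. An event that worsens after Day 7 without a break keeps its earlier, lower grade in the solicited table, and the only other graded incidence tables are closed to it.

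What is at stake is completeness of the severity profile in the clinical study report and in the Phase 2 interim analysis, which SAP 1.2 says will inform Phase 3 preparation. The reactions affected are prolonged or slow to peak. The omission also sits awkwardly with the safety estimand in SAP Table 2, whose stated strategy is that everything collected goes into the summaries.

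**Working it through.** The point concerns counting rules, and the plan attaches no figure to it. The check is to follow one event through every planned output that could show its grade.

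**Test case.** Swelling starts on Day 5 at Grade 2, is present every day, and first reaches Grade 3 on Day 9.

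| Planned output | Rule | Shown as Grade 3? |
|---|---|---|
| Solicited event table and composite rows (SAP 4.2.1.1) | Maximum grade in Day 1-7, here 2 | No, shown as Grade 2 |
| Grade 3 unsolicited table (SAP 4.2.1.2) | Ongoing solicited events not counted (SAP 6.2.2.4) | No |
| Grade 3 related unsolicited table (SAP 4.2.1.2) | Same exclusion | No |
| Combined solicited and unsolicited summary (SAP 6.2.1.10) | One event; no Grade 3 row described | No |
| Grade-specific duration summary (SAP 4.2.1.1) | Days at or above a grade in an undefined reporting period | Only if the period extends past Day 7; a duration, not an incidence |
| Holding-rule 2a number and percentage (SAP 4.5.1, Tables 5 and 6) | Onset in Day 1-7; the day on which Grade 3 is reached is not mentioned | Unclear; in Phase 2 also needs Grade 3 for 2 consecutive days |
| Listing (SAP 4.2.1.1) | Flag for continuing beyond Day 7 | Event flagged as prolonged, participant level only |

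**Limits of the gap.** It covers continuous events only. Under SAP 6.2.1.10, a symptom that stops and restarts after Day 7 is a new event and can enter the unsolicited tables. A serious or medically attended case can still enter the SAE or MAE tables, but those are not Grade 3 tables.

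**Are the data there?** SAP 4.2.1.1 defines the stop date of a solicited event as the last day with grade above 0 in or beyond the solicited period. That presupposes grades recorded after Day 7, so the later maximum can be derived from planned data.

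**Size per participant.**
- Phase 1 group, n = 24 (SAP 5.1): 1/24 = 4.2 percentage points.
- Phase 2 group, n = 120 (SAP 1.2): 1/120 = 0.8 percentage points.

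**Number of participants.** The documents give no frequency. Assuming 0 to 2% of participants, the expected number per group is 0 to 0.02 × 120 = 2.4 in Phase 2, and 0 to 0.02 × 24 = 0.48 in Phase 1. The range is an assumption and includes zero.

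**The case against.** The strongest reply is that nothing is wrong with the co-primary analysis. The endpoint is occurrence within 7 days, so a grade reached on Day 9 lies outside it and the Day 1-7 maximum measures exactly what was defined. That stands: the table does not understate its own endpoint. The gap is in the reporting around it.

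A second reply is that late worsening should be rare. Protocol 2.3 expects reactions within the first 3 days and resolution within a few days of onset. That also stands, and it is why the size may be near zero.

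A third is that the event is not lost. This is partly right: the listing will flag it, and the duration summary or the rule 2a tabulation may capture it. But the wording of those two outputs leaves it open, and a listing is not an incidence by group.

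A reader might go further and infer three things that the documents do not support.
- *That one missed participant could flip a tolerability decision.* With the Beta(0.5, 0.5) prior of SAP Table 7, 4 of 24 gives a 54.5% probability that the rate is below 18%, as the plan states, and 5 of 24 gives 34.1%. But that table illustrates sample-size precision. The 50% rule belongs to the Bayesian logistic regression model. In Protocol Table 28 (the one-slope model), 5 of 24 at the last-listed dose of scenario 2 has an overdose probability of 0.242. The line is crossed only in scenario 3, with 6 of 24 at 0.596.
- *That dose selection was affected.* The Phase 2 doses were already in Protocol Amendment 2 (28 Aug 2023), before the current SAP (30 Jan 2024). The model is used in Phase 1 only, and its text does not say which grading window feeds it.
- *That the comparison of mRNA with control is biased.* SAP Table 2 plans no treatment comparison for the safety estimand, and nothing in the documents shows that prolonged events differ by arm.

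**Conclusion.** The point holds as a narrow reporting gap created by two explicit rules. A continuous solicited event with onset by Day 7 that first reaches Grade 3 on Day 8-28 has no place in the planned solicited or unsolicited Grade 3 endpoint tables. The statement is confined to those tables, because the holding-rule 2a tabulation might include the case.

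The effect per participant is small in Phase 2 and larger in Phase 1, and the total may be zero. The conclusion rests on reading SAP 4.2.1.1 and 6.2.2.4 as written; it does not depend on the assumed frequency. It is a cheap improvement to the reporting, not a fault in the co-primary analysis.

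**What to change.** 1. Keep the Day 1-7 maximum-grade table in SAP 4.2.1.1 unchanged.
2. Add one supportive table by group. For each solicited event with onset in Day 1-7, give the number and percentage of participants by maximum grade from onset to resolution, at most Day 28, with rows for Grade 2 or above and Grade 3.
3. In SAP 6.2.2.4, keep the exclusion and cross-refer to the new table, so that it is clear where prolonged solicited events are reported.
4. In SAP 4.2.1.1, state that the reporting period for the grade-specific duration runs to Day 28.

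The cost is a few lines of SAP text and one more output from eDiary records already being collected. No new visits or data are needed. The downside is that reported Grade 3 severity may look slightly less favourable.
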